|----------------|------------------------|--|
| Grade 1 | No dose modifications. | 
For Grade 1:
 
 – Consider, as necessary, discussing with the study physician. – Care should be taken to monitor patients for sentinel symptoms of a potential decompensation as described above. – Obtain a neurology consult. |
|----------------|------------------------|--|

| | | |
|----------------|--|--|
| Grade 2 | 
Hold study drug/study regimen dose until resolution to Grade ≤ 1.
 
Permanently discontinue study drug/study regimen if it does not resolve to Grade ≤ 1 within 30 days or if there are signs of respiratory insufficiency or autonomic instability.
 | 
For Grade 2:
 
 – Consider, as necessary, discussing with the study physician. – Care should be taken to monitor patients for sentinel symptoms of a potential decompensation as described above. – Obtain a neurology consult – Sensory neuropathy/neuropathic pain may be managed by appropriate medications (e.g., gabapentin or duloxetine). |
|----------------|--|--|

MYASTHENIA GRAVIS:

- Steroids may be successfully used to treat myasthenia gravis. It is important to consider that steroid therapy (especially with high doses) may result in transient worsening of myasthenia and should typically be administered in a monitored setting under supervision of a consulting neurologist.
- Patients unable to tolerate steroids may be candidates for treatment with plasmapheresis or IV

IG. Such decisions are best made in consultation with a neurologist, taking into account the unique needs of each patient.

- If myasthenia gravis-like neurotoxicity is present, consider starting AChE inhibitor therapy in addition to steroids. Such therapy, if successful, can also serve to reinforce the diagnosis.

GUILLAIN-BARRE:

- It is important to consider here that the use of steroids as the primary treatment of Guillain-Barre is not typically considered effective.
- Patients requiring treatment should be started with IV IG and followed by plasmapheresis if not responsive to IV IG.

Grade 3 or 4

For Grade 3:

Hold study drug/study regimen dose until resolution to Grade ≤ 1 .

Permanently discontinue study drug/study regimen if Grade 3 imAE does not resolve to Grade ≤ 1 within 30 days or if there are signs of respiratory insufficiency or autonomic instability.

For Grade 4:

For Grade 3 or 4 (severe or life-threatening events):

- Consider, as necessary, discussing with study physician.
- Recommend hospitalization.
- Monitor symptoms and obtain neurological consult.

MYASTHENIA GRAVIS:

- Steroids may be successfully used to treat myasthenia gravis. They should typically be administered in a monitored setting under supervision of a consulting neurologist.

Permanently discontinue study drug/study regimen.

- Patients unable to tolerate steroids may be candidates for treatment with plasmapheresis or IV IG.
- If myasthenia gravis-like neurotoxicity present, consider starting AChE inhibitor therapy in addition to steroids. Such therapy, if successful, can also serve to reinforce the diagnosis.

GUILLAIN-BARRE:

- It is important to consider here that the use of steroids as the primary treatment of Guillain-Barre is not typically considered effective.
- Patients requiring treatment should be started with IV IG and followed by plasmapheresis if not responsive to IV IG.

| Myocarditis | Any Grade | General Guidance | For Any Grade: |
|-------------|-----------|--|--|
| | | Discontinue drug permanently if biopsy-proven immune-mediated myocarditis. | 
 – The prompt diagnosis of immune-mediated myocarditis is important, particularly in patients with baseline cardiopulmonary disease and reduced cardiac function. – Consider, as necessary, discussing with the study physician. – Monitor patients for signs and symptoms of myocarditis (new onset or worsening chest pain, arrhythmia, shortness of breath, peripheral edema). As some symptoms can overlap with lung toxicities, simultaneously |

evaluate for and rule out pulmonary toxicity as well as other causes (e.g., pulmonary embolism, congestive heart failure, malignant pericardial effusion). A Cardiology consultation should be obtained early, with prompt assessment of whether and when to complete a cardiac biopsy, including any other diagnostic procedures.

- Initial work-up should include clinical evaluation, BNP, cardiac enzymes, ECG, echocardiogram (ECHO), monitoring of oxygenation via pulse oximetry (resting and exertion), and additional laboratory work-up as indicated. Spiral CT or cardiac MRI can complement ECHO to assess wall motion abnormalities when needed.
- Patients should be thoroughly evaluated to rule out any alternative etiology (e.g., disease progression, other medications, or infections).

Grade 1
(asymptomatic with laboratory (e.g., BNP) or cardiac imaging abnormalities)

No dose modifications required unless clinical suspicion is high, in which case hold study drug/study regimen dose during diagnostic work-up for other etiologies. If study drug/study regimen is held, resume after complete resolution to Grade 0.

For Grade 1 (no definitive findings):

- Monitor and closely follow up in 2 to 4 days for clinical symptoms, BNP, cardiac enzymes, ECG, ECHO, pulse oximetry (resting and exertion), and laboratory work-up as clinically indicated.
- Consider using steroids if clinical suspicion is high.

Grade 2, 3 or 4
(Grade 2: Symptoms with mild to moderate activity or exertion)

(Grade 3: Severe with symptoms at rest)

- If Grade 2 -- Hold study drug/study regimen dose until resolution to Grade 0. If toxicity rapidly improves to Grade 0, then the decision to reinstate study drug/study regimen

For Grade 2-4:

- Monitor symptoms daily, hospitalize.
- Promptly start IV methylprednisolone 2 to 4 mg/kg/day or equivalent after Cardiology consultation has determined whether and when to

| | | |
|---|--|---|
| 
or with minimal activity or exertion; intervention indicated)
 
(Grade 4: Life-threatening consequences; urgent intervention indicated (e.g., continuous IV therapy or mechanical hemodynamic support))
 | 
will be based upon treating physician's clinical judgment and after completion of steroid taper. If toxicity does not rapidly improve, permanently discontinue study drug/study regimen.
 
If Grade 3-4, permanently discontinue study drug/study regimen.
 | 
complete diagnostic procedures including a cardiac biopsy.
 
 - Supportive care (e.g., oxygen). - If no improvement within 3 to 5 days despite IV methylprednisolone at 2 to 4 mg/kg/day, promptly start immunosuppressive therapy such as TNF inhibitors (e.g., infliximab at 5 mg/kg every 2 weeks). Caution: It is important to rule out sepsis and refer to infliximab label for general guidance before using infliximab. - Once the patient is improving, gradually taper steroids over ≥ 28 days and consider prophylactic antibiotics, antifungals, or anti-PJP treatment (refer to current NCCN guidelines for treatment of cancer-related infections [Category 2B recommendation]).^a |
|---|--|---|

| Myositis/Polymyositis ("Poly/myositis") | Any Grade | General Guidance | For Any Grade: |
|---|-----------|------------------|---|
| | | | 
 - Monitor patients for signs and symptoms of poly/myositis. Typically, muscle weakness/pain occurs in proximal muscles including upper arms, thighs, shoulders, hips, neck and back, but rarely affects the extremities including hands and fingers; also difficulty breathing and/or trouble swallowing can occur and progress rapidly. Increased general feelings of tiredness and fatigue may occur, and there can be new-onset falling, difficulty getting up from a fall, and trouble climbing stairs, standing up from a seated position, and/or reaching up. - If poly/myositis is suspected, a Neurology consultation should be obtained early, with prompt guidance on diagnostic procedures. Myocarditis may co-occur with poly/myositis; refer to |

guidance under Myocarditis.
Given breathing complications,
refer to guidance under
Pneumonitis/ILD.

Given possibility of an existent
(but previously unknown)
autoimmune disorder, consider
Rheumatology consultation.

- Consider, as necessary,
discussing with the study
physician.
- Initial work-up should include
clinical evaluation, creatine
kinase, aldolase, LDH,
BUN/creatinine, erythrocyte
sedimentation rate or C-reactive
protein level, urine myoglobin,
and additional laboratory work-
up as indicated, including a
number of possible
rheumatological/antibody tests
(i.e., consider whether a
rheumatologist consultation is
indicated and could guide need
for rheumatoid factor, antinuclear
antibody, anti-smooth muscle,
antisynthetase [such as anti-Jo-1],
and/or signal-recognition particle
antibodies). Confirmatory testing
may include electromyography,
nerve conduction studies, MRI of
the muscles, and/or a muscle
biopsy. Consider Barium
swallow for evaluation of
dysphagia or dysphonia.

Patients should be thoroughly evaluated to
rule out any alternative etiology (e.g.,
disease progression, other medications, or
infections).

Grade 1
(mild pain)

- No dose
modifications.

For Grade 1:

- Monitor and closely follow up in
2 to 4 days for clinical symptoms
and initiate evaluation as
clinically indicated.
- Consider Neurology consult.

Grade 2
(moderate pain associated with weakness; pain limiting instrumental activities of daily living [ADLs])

Hold study drug/study regimen dose until resolution to Grade ≤ 1 .

- Permanently discontinue study drug/study regimen if it does not resolve to Grade ≤ 1 within 30 days or if there are signs of respiratory insufficiency.

- Consider, as necessary, discussing with the study physician.

For Grade 2:

- Monitor symptoms daily and consider hospitalization.
- Obtain Neurology consult, and initiate evaluation.
- Consider, as necessary, discussing with the study physician.
- If clinical course is rapidly progressive (particularly if difficulty breathing and/or trouble swallowing), promptly start IV methylprednisolone 2 to 4 mg/kg/day systemic steroids along with receiving input from Neurology consultant.
- If clinical course is *not* rapidly progressive, start systemic steroids (e.g., prednisone 1 to 2 mg/kg/day PO or IV equivalent); if no improvement within 3 to 5 days, continue additional work up and start treatment with IV methylprednisolone 2 to 4 mg/kg/day
- If after start of IV methylprednisolone at 2 to 4 mg/kg/day there is no improvement within 3 to 5 days, consider start of immunosuppressive therapy such as TNF inhibitors (e.g., infliximab at 5 mg/kg every 2 weeks). Caution: It is important to rule out sepsis and refer to infliximab label for general guidance before using infliximab.
- Once the patient is improving, gradually taper steroids over ≥ 28 days and consider prophylactic antibiotics, antifungals, or anti-PJP treatment (refer to current NCCN guidelines for treatment of cancer-related infections)

[Category 2B
recommendation]).^a

| | | |
|--|--|---|
| 
Grade 3 or 4 (pain associated with severe weakness; limiting self-care ADLs)
 | 
For Grade 3: Hold study drug/study regimen dose until resolution to Grade ≤1. Permanently discontinue study drug/study regimen if Grade 3 imAE does not resolve to Grade ≤1 within 30 days or if there are signs of respiratory insufficiency.
 
For Grade 4: - Permanently discontinue study drug/study regimen.
 | 
For Grade 3 or 4 (severe or life-threatening events):
 
 - Monitor symptoms closely; recommend hospitalization. - Obtain Neurology consult, and complete full evaluation. - Consider, as necessary, discussing with the study physician. - Promptly start IV methylprednisolone 2 to 4 mg/kg/day systemic steroids along with receiving input from Neurology consultant. - If after start of IV methylprednisolone at 2 to 4 mg/kg/day there is no improvement within 3 to 5 days, consider start of immunosuppressive therapy such as TNF inhibitors (e.g., infliximab at 5 mg/kg every 2 weeks). Caution: It is important to rule out sepsis and refer to infliximab label for general guidance before using infliximab. - Consider whether patient may require IV IG, plasmapheresis. - Once the patient is improving, gradually taper steroids over ≥28 days and consider prophylactic antibiotics, antifungals, or anti-PJP treatment (refer to current NCCN guidelines for treatment of cancer-related infections 
[Category 2B recommendation]).^a
 |
|--|--|---|

^aASCO Educational Book 2015 “Managing Immune Checkpoint Blocking Antibody Side Effects” by Michael Postow MD.

^bFDA Liver Guidance Document 2009 Guidance for Industry: Drug Induced Liver Injury – Premarketing Clinical Evaluation. AChE Acetylcholine esterase; ADL Activities of daily living; AE Adverse event; ALP Alkaline phosphatase test; ALT Alanine aminotransferase; AST Aspartate aminotransferase; BUN Blood urea nitrogen; CT Computed tomography; CTCAE Common Terminology Criteria for Adverse Events; ILD Interstitial lung disease; imAE immune-mediated adverse event; IG Immunoglobulin; IV Intravenous; GI Gastrointestinal; LFT Liver function tests; LLN Lower limit of normal; MRI Magnetic resonance imaging; NCI National Cancer Institute; NCCN National Comprehensive Cancer Network; PJP *Pneumocystis jirovecii* pneumonia (formerly known as *Pneumocystis carinii* pneumonia); PO By mouth; T3 Triiodothyronine; T4 Thyroxine; TB Total bilirubin; TNF Tumor necrosis factor; TSH Thyroid-stimulating hormone; ULN Upper limit of normal.

Infusion-Related Reactions

| Severity Grade of the Event (NCI CTCAE version 4.03) | Dose Modifications | Toxicity Management |
|--|--|--|
| Any Grade | General Guidance | 
For Any Grade:
 
 – Manage per institutional standard at the discretion of investigator. – Monitor patients for signs and symptoms of infusion-related reactions (e.g., fever and/or shaking chills, flushing and/or itching, alterations in heart rate and blood pressure, dyspnea or chest discomfort, or skin rashes) and anaphylaxis (e.g., generalized urticaria, angioedema, wheezing, hypotension, or tachycardia). |
| Grade 1 or 2 | 
For Grade 1:
 
The infusion rate of study drug/study regimen may be decreased by 50% or temporarily interrupted until resolution of the event.
 
For Grade 2:
 
The infusion rate of study drug/study regimen may be decreased 50% or temporarily interrupted until resolution of the event.
 
Subsequent infusions may be given at 50% of the initial infusion rate.
 | 
For Grade 1 or 2:
 
 – Acetaminophen and/or antihistamines may be administered per institutional standard at the discretion of the investigator. – Consider premedication per institutional standard prior to subsequent doses. – Steroids should not be used for routine premedication of Grade ≤ 2 infusion reactions. |
| Grade 3 or 4 | 
For Grade 3 or 4:
 
Permanently discontinue study drug/study regimen.
 | 
For Grade 3 or 4:
 
 – Manage severe infusion-related reactions per institutional standards (e.g., IM epinephrine, followed by IV diphenhydramine and ranitidine, and IV glucocorticoid). |

CTCAE Common Terminology Criteria for Adverse Events; IM intramuscular; IV intravenous; NCI National Cancer Institute.

Non-Immune-Mediated Reactions

| Severity Grade of the Event (NCI CTCAE version 4.03) | Dose Modifications | Toxicity Management |
|--|---|---|
| Any Grade | Note: Dose modifications are not required for AEs not deemed to be related to study treatment (i.e., events due to underlying disease) or for laboratory abnormalities not deemed to be clinically significant. | Treat accordingly, as per institutional standard. |
| Grade 1 | No dose modifications. | Treat accordingly, as per institutional standard. |
| Grade 2 | Hold study drug/study regimen until resolution to \leq Grade 1 or baseline. | Treat accordingly, as per institutional standard. |
| Grade 3 | Hold study drug/study regimen until resolution to \leq Grade 1 or baseline. For AEs that downgrade to \leq Grade 2 within 7 days or resolve to \leq Grade 1 or baseline within 14 days, resume study drug/study regimen administration. Otherwise, discontinue study drug/study regimen. | Treat accordingly, as per institutional standard. |
| Grade 4 | Discontinue study drug/study regimen (Note: For Grade 4 labs, decision to discontinue should be based on accompanying clinical signs/symptoms, the Investigator's clinical judgment, and consultation with the Sponsor.). | Treat accordingly, as per institutional standard. |

Note: As applicable, for early phase studies, the following sentence may be added: "Any event greater than or equal to Grade 2, please discuss with Study Physician."

AE Adverse event; CTCAE Common Terminology Criteria for Adverse Events; NCI National Cancer Institute.

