14. Radiotherapy, chemotherapy, or other anti-neoplastic therapy within 14 days prior to start of study drug (C1D1), except shorter if approved by the Sponsor
15. Major surgery within 28 days prior to start of study drug (C1D1), except shorter if approved by the Sponsor. Note: Local surgery of isolated lesions for palliative intent is acceptable
16. Use of any other experimental medication within 14 days prior to start of study drug (C1D1)
17. Planned live vaccine administration after starting study drug (C1D1)
18. Failure to recover to Grade ≤ 1 (Common Terminology Criteria for Adverse Events [CTCAE] version 4.0) from acute non-hematologic toxicity (Grade ≤ 2 neuropathy or alopecia) due to previous therapy prior to screening
19. Congenital long QT syndrome or a corrected QTcF interval of >470 ms at screening (unless secondary to pacemaker or bundle branch block)
20. History of another primary malignancy except for:
 - a. Malignancy treated with curative intent and with no known active disease ≥ 5 years before the first dose of investigational product and of low potential risk for recurrence
 - b. Adequately treated non-melanoma skin cancer or lentigo maligna without evidence of disease
 - c. Adequately treated carcinoma in situ without evidence of disease
21. History of active primary immunodeficiency
22. Any other significant medical illness, abnormality, or condition that would, in the Investigator's judgement, make the patient inappropriate for study participation or put the patient at risk.

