6.5.2 Durvalumab

If a patient experiences any Grade ≥ 3 toxicity, durvalumab must be held until the toxicity resolves to Grade 1 or less (Grade 1 or baseline for peripheral neuropathy).

In addition, durvalumab must be held for the following Grade ≥ 2 specific immune-mediated toxicities:

- Pneumonitis/ILD
- Diarrhea/Colitis
- Hepatitis (elevated liver function tests)
- Nephritis or renal dysfunction
- Persistent rash (>1 -2 weeks)
- Endocrinopathy (except isolated hypothyroidism or Type 1 diabetes mellitus)
- Neurotoxicity
- Peripheral neuromotor syndromes
- Myocarditis
- Myositis/polymyositis

See [Section 13.3](#), [Appendix 3](#) for guidelines regarding management and resumption of durvalumab therapy after specific immune-mediated toxicities.

For all other toxicities, durvalumab must be held until the toxicity resolves to Grade 1 or less (Grade 1 or baseline for peripheral neuropathy).

Durvalumab will be given at full dose when resumed after being held for toxicity, i.e., there will be no dose reduction.

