| 
(to include but not be limited to limbic encephalitis and autonomic neuropathy, excluding Myasthenia Gravis and Guillain-Barre)
 | 
(depending on the type of neurotoxicity, refer to NCI CTCAE v4.03 for defining the CTC grade/severity)
 | | 
 – Patients should be evaluated to rule out any alternative etiology (e.g., disease progression, infections, metabolic syndromes, or medications). – Monitor patient for general symptoms (headache, nausea, vertigo, behavior change, or weakness). – Consider appropriate diagnostic testing (e.g., electromyogram and nerve conduction investigations). |

| | | |
|---------------------|--|--|
| | | 
 - Perform symptomatic treatment with neurological consult as appropriate. - |
| Grade 1 | No dose modifications. | 
For Grade 1:
 
 - See “Any Grade” recommendations above. |
| Grade 2 | 
For acute motor neuropathies or neurotoxicity, hold study drug/study regimen dose until resolution to Grade ≤ 1.
 
For sensory neuropathy/neuropathic pain, consider holding study drug/study regimen dose until resolution to Grade ≤ 1.
 
If toxicity worsens, then treat as Grade 3 or 4.
 
Study drug/study regimen can be resumed once event improves to Grade ≤ 1 and after completion of steroid taper.
 | 
For Grade 2:
 
 - Consider, as necessary, discussing with the study physician. - Obtain neurology consult. - Sensory neuropathy/neuropathic pain may be managed by appropriate medications (e.g., gabapentin or duloxetine). - Promptly start systemic steroids prednisone 1 to 2 mg/kg/day PO or IV equivalent. - If no improvement within 3 to 5 days despite 1 to 2 mg/kg/day prednisone PO or IV equivalent, consider additional workup and promptly treat with additional immunosuppressive therapy (e.g., IV IG). |

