| Grade 3 or 4 | 
For Grade 3:
 
Hold study drug/study regimen dose until resolution to Grade ≤ 1.
 
Permanently discontinue study drug/study regimen if Grade 3 imAE does not resolve to Grade ≤ 1 within 30 days.
 
For Grade 4:
 
Permanently discontinue study drug/study regimen.
 | 
For Grade 3 or 4:
 
 - Consider, as necessary, discussing with study physician. - Obtain neurology consult. - Consider hospitalization. - Promptly initiate empiric IV methylprednisolone 1 to 2 mg/kg/day or equivalent. - If no improvement within 3 to 5 days despite IV corticosteroids, consider additional workup and promptly treat with additional immunosuppressants (e.g., IV IG). - Once stable, gradually taper steroids over ≥ 28 days. |
| Any Grade | General Guidance | For Any Grade: |

Peripheral neuromotor syndromes

(such as Guillain-Barre and myasthenia gravis)

- The prompt diagnosis of immune-mediated peripheral neuromotor syndromes is important, since certain patients may unpredictably experience acute decompensations that can result in substantial morbidity or in the worst case, death. Special care should be taken for certain sentinel symptoms that may predict a more severe outcome, such as prominent dysphagia, rapidly progressive weakness, and signs of respiratory insufficiency or autonomic instability.
 - Patients should be evaluated to rule out any alternative etiology (e.g., disease progression, infections, metabolic syndromes or medications). It should be noted that the diagnosis of immune-mediated peripheral neuromotor syndromes can be particularly challenging in patients with underlying cancer, due to the multiple potential confounding effects of cancer (and its treatments) throughout the neuraxis. Given the importance of prompt and accurate diagnosis, it is essential to have a low threshold to obtain a neurological consult.
 - Neurophysiologic diagnostic testing (e.g., electromyogram and nerve conduction investigations, and “repetitive stimulation” if myasthenia is suspected) are routinely indicated upon suspicion of such conditions and may be best facilitated by means of a neurology consultation.
 - It is important to consider that the use of steroids as the primary treatment of Guillain-Barre is not typically considered effective. Patients requiring treatment should be started with IV IG and
-

followed by plasmapheresis if not responsive to IV IG.

| | | |

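### Section 6.5.2 requires a durvalumab hold for Grade 2 immune-mediated sensory neuropathy and Appendix 3 makes it optional; at Grade 3 their return conditions also conflict for patients who enter with Grade 2 neuropathy

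*Protocol*

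**What the plan says.** Protocol Section 6.5.2 opens with a general rule: for any toxicity of Grade 3 or higher, "durvalumab must be held until the toxicity resolves to Grade 1 or less (Grade 1 or baseline for peripheral neuropathy"). It then adds a list: "In addition, durvalumab must be held for the following Grade ≥ 2 specific immune-mediated toxicities". Neurotoxicity is on that list without qualification. Next, 6.5.2 refers the reader to Appendix 3 "for guidelines regarding management and resumption of durvalumab therapy after specific immune-mediated toxicities". It closes by repeating the Grade 1 or baseline wording for all other toxicities, and it rules out durvalumab dose reduction.

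The Neurotoxicity row of Appendix 3 (Section 13.3) divides Grade 2 events in two. For the first group: "For acute motor neuropathies or neurotoxicity, hold study drug/study regimen dose until resolution to Grade" 1 or less. For the second: "For sensory neuropathy/neuropathic pain, consider holding study drug/study regimen dose" until the same level is reached. Resumption needs Grade 1 or less and a completed steroid taper. At Grade 3 the row says: "Permanently discontinue study drug/study regimen if Grade 3 imAE does not resolve to Grade" 1 or less within 30 days. No Grade 2 or Grade 3 entry in this row mentions baseline.

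Exclusion criterion 18 (Section 5.2 and synopsis) requires recovery to Grade 1 or less from earlier toxicity, but tolerates Grade 2 or less "neuropathy or alopecia) due to previous therapy prior to screening".

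**The concern.** An investigator who sees a Grade 2 immune-mediated sensory neuropathy on the day durvalumab is due finds a *must* in the body of the protocol and a *consider* in the appendix to which the body points. If the event is Grade 3 in a patient who already had Grade 2 neuropathy on entry, recovery to the entry grade meets one text's condition for resuming and, once 30 days have passed, the other text's condition for a permanent stop.

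Beyond the individual dosing decision, three outputs depend on which text is followed:

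- Frequency of dose interruptions and reductions is a primary endpoint (synopsis; Protocol Table 2). Durvalumab is never reduced, so for that drug the endpoint comes down to interruptions.
- SAP Section 4.8.2.1 summarises adverse events leading to discontinuation or dose modification separately for each drug.
- A dose given during Grade 2 sensory neuropathy departs from 6.5.2 but not from Appendix 3. The predefined deviations in SAP Section 4.3 do not name this case.

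**Working it through.** No sample size, power or rate figure is involved, so the check sets the texts side by side.

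| Immune-mediated event | Section 6.5.2 | Appendix 3, Neurotoxicity row | Result |
|---|---|---|---|
| Grade 2, acute motor neuropathy or neurotoxicity: hold? | Mandatory | Hold | Agree |
| Grade 2, sensory neuropathy or neuropathic pain: hold? | Mandatory | Optional | Conflict |
| Grade 2: return condition | None stated for listed events; refers to Appendix 3 | Grade 1 or less, steroid taper complete | Gap on baseline, no conflict |
| Grade 3 peripheral neuropathy: return condition | Grade 1 or baseline | Grade 1 or less within 30 days, otherwise permanent stop | Conflict if baseline is Grade 2 |

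**Grade 2 hold.** Two features of 6.5.2 make it hard to treat its list as shorthand that leaves exceptions to the appendix. The cross-reference covers management and resumption, which come after the decision to hold. The list also carries other appendix exceptions forward: rash is limited to persistent rash, and endocrinopathy excludes isolated hypothyroidism and Type 1 diabetes. The sensory exception is not carried forward.

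**Grade 3 return.** Let b be the neuropathy grade at entry and g the grade reached by day 30.

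- Section 6.5.2 is met if g ≤ 1 or g ≤ b, that is, g ≤ max(1, b).
- Appendix 3 is met if g ≤ 1.
- If b is 0 or 1, max(1, b) = 1 and the grade thresholds coincide.
- If b = 2, the highest grade that exclusion 18 allows, 6.5.2 accepts g ≤ 2 and Appendix 3 accepts g ≤ 1. They disagree only when g = 2.

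Such a patient may resume under 6.5.2 and must stop permanently under Appendix 3, unless the neuropathy becomes one grade better than at entry.

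**Reach.** The Grade 3 stop is worded for an immune-mediated event, and the row asks that other causes be ruled out. Worsening that is not immune-mediated falls under the closing rule of 6.5.2 and the appendix's separate table for non-immune reactions. Both contain a baseline clause.

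**DLT window.** The window is the 21 days after the first durvalumab dose (Section 6.4.2). That dose is on C1D8 and the next on C2D15. Cycle 1 lasts 21 days, so C2D15 is study day 21 + 15 = 36, which is 36 − 8 = 28 days after the first dose. With the ±2-day visit window used in full at both ends, the gap is still 28 − 4 = 24 days. No scheduled durvalumab dose falls inside the window, and DLT status is set by Section 6.4.3, not by these rows.

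**The case against.** The best defence is that resumption after specific immune-mediated toxicities is expressly delegated to Appendix 3, so the appendix overrides the general Grade 3 sentence as the more specific text. This is a fair reading, and at Grade 2 it succeeds: 6.5.2 sets no return threshold there for listed events, so the missing baseline option is a gap. At Grade 3 the opening sentence of 6.5.2 covers any toxicity and contains its own baseline clause. No statement of precedence says that it yields.

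It can also be said that a site which always holds at Grade 2 complies with both texts. That is true, but a site which doses complies with only one, so the conflict remains.

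A reader might infer that the baseline clause was left out of the Neurotoxicity row by mistake, because the hepatitis, nephritis and rash rows have one. The pneumonitis, diarrhea/colitis, peripheral neuromotor and myositis rows have none, so its absence proves nothing about intent.

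Finally, the trial was terminated early and only Part 1 data will be analysed (SAP Section 3.3). This limits what an amendment can still change in conduct. It does not remove the inconsistency or settle how Part 1 interruptions, discontinuations and deviations should be classified.

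**Conclusion.** The Grade 2 conflict is direct: one text mandates a durvalumab hold for immune-mediated sensory neuropathy and the other leaves it to judgement. The Grade 3 conflict is real but narrow. It needs entry at Grade 2, an immune-mediated worsening to Grade 3, and recovery that stops at Grade 2. It rests on reading the opening sentence of 6.5.2 as applying to listed immune-mediated events, which its wording supports and nothing in the section excludes.

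The size cannot be estimated. The documents give neither the prevalence of neuropathy at entry nor the rate of immune-mediated neuropathy; both conflicts are probably uncommon.

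Several larger conclusions might be inferred but are not supported:

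- *Every patient with Grade 2 neuropathy at entry who reaches Grade 3 is affected.* Worsening that is not immune-mediated has a baseline clause throughout.
- *Permanent discontinuation is part of the primary endpoint.* The endpoint names interruptions and reductions; discontinuation appears in the adverse event summaries.
- *The combination must be stopped.* Appendix 3 gives durvalumab guidelines, and loncastuximab tesirine has its own rule in Section 6.5.1. The appendix's mention of the study regimen is ambiguous, but does not establish this.
- *Tolerability rates or dose escalation would shift materially.* One patient is 1/6 = 16.7 or 1/3 = 33.3 percentage points of a dose level of 6 or 3, but that is only the weight of one patient, not an expected effect. No route to DLT assessment or escalation is shown.

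**What to change.** Reconcile Section 6.5.2 and the Neurotoxicity row of Appendix 3 so that together they give:

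1. One instruction on whether durvalumab is held for Grade 2 immune-mediated sensory neuropathy or neuropathic pain.
2. One return condition, stating how a patient with Grade 2 neuropathy at entry under exclusion 18 is handled at Grade 2 and at Grade 3.
3. A statement of which text governs if the two differ.

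The sponsor chooses the clinical rule. The cost is wording in one appendix row and in 6.5.2, by amendment or clarification letter, with no new data. Because the trial has ended early, the immediate use is for Part 1 reporting: record which text was applied to any such event when classifying interruptions, discontinuations and deviations. Correct the wording before it is reused in another protocol.
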